8.1 Primary Endpoint

For Phase 1 of this protocol, the primary endpoint is the percent of adverse events that develop in the study group at each studied dose of ALA.

For Phase 2 of this protocol, the primary endpoint is the mean rate of change of the area of GA in the study eye from baseline to 18 months (from the time of randomization) as evaluated by fundus autofluorescence.

8.2 Secondary Endpoints

A secondary endpoint for Phase I is the percent of subjects that think they could tolerate each studied dose of ALA for a duration of 18 months. If 4 or more (out of 15) subjects state that they could not imagine taking a particular dose for 18 months, then that dose will not be used in the Phase 2 Trial.

The secondary endpoints for Phase 2 include:

- The change in best corrected visual acuity (BCVA) from baseline to 18 months from the time of randomization

CONFIDENTIAL

- The proportion of subjects with three lines or more worsening in BCVA
 - Absolute and relative change in area of GA as measured on FAF
 - Rate of change over time (18 months from the time of randomization) in area of GA in the study eye as measured on color fundus photos.
 - Absolute and relative change in area of GA as measured on color fundus photos
 - Change in drusen volume based on OCT and change in the number of drusen seen on color fundus photos (exploratory endpoint)
 - Change in score on the Ocular Surface Disease Index (OSDI)⁴⁷ (exploratory endpoint)
 - Change in best distance corrected near visual acuity (exploratory endpoint)
- Ocular and systemic safety outcomes for these doses of ALA

8.3 Sample Size and Power Determination

Phase 1: It is expected that a sample size of 15 subjects will adequately determine if there is a significant intolerance of the tested doses of ALA in the elderly population.

Phase 2: In addition to assessing the safety profile of ALA and the feasibility of study procedures, one of the major goals of the proposed study is to determine if additional, larger scale assessments of efficacy are warranted. For pilot studies, it is appropriate to use a confidence interval approach to evaluate outcomes and pre-specify a clinically important threshold to determine if further investigation is justified.⁵⁰⁻⁵¹ If we decide to halt investigation if the observed growth rate in the actively treated group is greater than in the placebo group, then it is reasonable to use a one-sided confidence interval. With 50 total subjects, we can be 90% confident (one-sided) that the “effect size” of ALA in reducing the GA growth rate is 0.4 or less. This number assumes that 15% of subjects dropout. An example of an effect size of 0.4 would be a growth rate of 0.40 mm in the placebo group and a growth rate of 0.32 (20% reduction) in the ALA group when the standard deviation of the annual growth rate is 0.20 mm.⁵² Interventions with less efficacy than this may not be worth pursuing.

Based on current data, it is possible that approximately 25% of subjects randomized to the ALA arm may not tolerate 1200 mg of ALA. Instead of 1200 mg once daily of ALA, some of these patients may elect to take 600 mg twice daily or 600 mg once daily. An intention to treat analysis will be performed on all subjects randomized to 1200 mg ALA in comparison to the placebo group. Subgroup analyses will be performed on those subjects remaining at 1200 mg and subjects at a lower dose of ALA. After 25 subjects have enrolled in the study, we will perform interim analyses of the numbers of subjects in these subgroups without evaluating any outcomes data. Depending on the status of enrollment, drop-out rates, and the size of the subgroup consistently taking 1200 mg subgroup, the study sample size may be increased at this time so that the 1200 mg subgroup has a number equal to or nearly equal to 22 subjects available for analyses.

8.4 Statistical Methods

Phase 1: Percentages of adverse events will be calculated.

Phase 2: As a preliminary analysis, the mean change in the total area of GA within study eyes over 18 months (from the time of randomization) will be compared between eyes receiving the active ALA dose and placebo supplementation; a square root transformation will be applied to the area measurements to mitigate the dependence of growth rate on initial size.⁵³⁻⁵⁴ Also, mean change in visual acuity over 18 months, the proportion with a decrease of 15 letters (3 lines) of visual acuity, and the proportions with serious adverse events will also be compared. Variants of the independent t-test and chi-square tests of proportions that account for the correlation between eyes of subjects who have two study eyes will be used to make comparisons.

The main analysis for comparing treatment groups will compare the rates of change in total area of GA using a mixed effects linear model. Use of this model allows including all patients in the analysis and requires less stringent assumptions than a complete cases analysis regarding the association of

CONFIDENTIAL

missingness with the outcome variable and does not introduce bias into the estimation of the slope parameter as a “last observation carried forward (LOCF)” approach does when area changes with time. Both subject and eye will be considered random effects. A sensitivity analysis using multiple imputation for missing values will be used for the analysis of mean change between baseline and 18 months and for the mixed effects linear model of total area.

Similar analytic methods using mixed effects models will be used for the other outcome measures.

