AMD is characterized by a progressive degeneration of the macula, leading to a severe decrease in central vision. An early sign of AMD is the appearance of drusen, which are yellow, extracellular deposits that accumulate below the retinal pigment epithelium (RPE) and are known to be risk factors for developing choroidal neovascularization (CNV). Depending on the number and size of drusen at the macula, a subject may be categorized as intermediate AMD.¹⁹ Some of these subjects may progress to advanced AMD. There are two types of advanced AMD: GA and exudative (neovascular) AMD. GA can be defined as one or more well-defined, more or less circular patches of loss of the RPE, typically with exposure of underlying choroidal blood vessels. GA can be multifocal or unifocal. Areas of GA are atrophic, nonfunctioning retina, and each area of GA leads to a scotoma in the subject's visual field. Exudative AMD is defined as the presence of abnormal vessels, referred to as choroidal neovascularization, under the retina or retinal pigment epithelium. These vessels can leak fluid and bleed, leading to acute and severe vision loss. The current standard-of-care treatment of exudative AMD is intravitreal injection therapy with anti-VEGF (vascular endothelial growth factor) agents.²⁰ For eyes with geographic atrophy, 2 – 18% may develop CNV over the course of two years, and CNV in the fellow eye is a risk factor for this development.²¹ There currently is no treatment to prevent or slow the progression of GA.

Several Phase I and Phase II clinical trials have evaluated agents targeting the mechanisms of GA,²²⁻²⁶ but there has been very limited success. Stem cell therapy holds promise but is an area where more work is needed to clearly show safety and efficacy in humans.²⁷⁻²⁸ Thus far, the only therapeutic agent that has progressed to a Phase III trial is lampalizumab, an inhibitor of complement factor D, and this trial

CONFIDENTIAL

is estimated to be complete in 2018.²⁹⁻³⁰ If lampalizumab is shown to be an effective treatment for GA, then there is still a significant need for other treatments for GA that may add to its effect or reduce its treatment burden, especially since lampalizumab may require intravitreal injection every 4 or 6 weeks. Thus, there is a critical need to find a treatment for GA that can slow its progression or prevent its onset. In the absence of such a treatment, a tremendous number of people will continue to become legally blind.

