4.2 Randomized, double-blind placebo controlled trial (Phase 2)

4.2.1 Inclusion Criteria

- Age 55-90
- Diagnosis of geographic atrophy from age-related macular degeneration in the study eye. The largest GA lesion must be a minimum of 0.5 DA (1.25 mm²) and no more than 6 DA in size (15.0 mm²). GA is defined as one or more well-defined, usually more or less circular patches of loss of the RPE, typically with exposure of underlying choroidal blood vessels. If the GA is multifocal and the largest lesion is < 0.5 DA, then there should be at least 3 lesions ≥ 250 microns in greatest linear diameter.
- BCVA between 20/20 and 20/400 in the study eye.
- Female participants must be menopausal. Male participants are required to use contraception and cannot donate sperm during study participation.
- Presence of hyperfluorescence at the edge of GA on autofluorescence imaging.

CONFIDENTIAL

This material is the property of the University of Pennsylvania.

- Ability to give informed consent.
- If a subject has two eligible eyes, then both eyes can be enrolled into the study.
- Subject must have mailed back the medication bottle after the 10 day run-in phase, demonstrating that they have taken $\geq 80\%$ of the capsules.

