Geographic atrophy (GA) will be assessed from the color fundus photographs and FAF images. On color photographs, GA is observed as one or more sharply defined, more or less circular patches of absence of the RPE, typically with exposure of underlying large choroidal blood vessels. At a minimum, at least two of the aforementioned characteristics (sharp edges, more or less circular shape and visibility of underlying choroidal vessels) with a minimum size of ≥ 175 microns in longest linear dimension are required for a lesion to be categorized as GA.⁴⁹ While a minimum size of ≥ 175 microns in longest linear dimension is required for a lesion to be categorized as GA for grading once an eye is in the study, the GA size requirements for study eye inclusion stated in section 4.2.1 (Inclusion Criteria) still stand.

Once geographic atrophy has been identified on the color photographs and FAF by the grader, the grader will use the Region Finder semi-automated software of the Heidelberg Spectralis to measure the areas of geographic atrophy at the macula of the study eye. While the color photographs are used to categorize a lesion as GA, the primary measure of GA area will be taken from the FAF images. The color photos can also be used to assist in the interpretation of the FAF images. GA appears as well defined hypoautofluorescent patches in FAF images. All areas of GA at the macula of the study eye will be measured.

CONFIDENTIAL

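### The square root of total GA area still depends on the number of lesions; adjusting for baseline focality could gain precision at little cost

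*Combined protocol and SAP*

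**What the plan says.** **Endpoint.** Section 7.2.3 (Geographic Atrophy) states that "All areas of GA at the macula of the study eye will be measured", so each eye contributes one total summed over its lesions.

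**Analysis.** In 8.4 the preliminary comparison is of mean change over 18 months, where "a square root transformation will be applied to the area measurements to mitigate the dependence of growth rate on initial size". The Study Summary says the same. The main analysis will "compare the rates of change in total area of GA using a mixed effects linear model". That sentence does not repeat the square root, although the growth rates in 8.3 are in mm, which suggests that scale. On model terms, 8.4 says "Both subject and eye will be considered random effects" and names no baseline covariate.

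**Entry.** Section 1.1 notes that "GA can be multifocal or unifocal". Section 4.2.1 requires the largest lesion to be between 0.5 and 6 DA (1.25 to 15.0 mm²) and sets no limit on the number of other lesions. A multifocal eye whose largest lesion is below 0.5 DA also qualifies; for it, "then there should be at least 3 lesions ≥ 250 microns in greatest linear diameter".

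**Randomization.** Section 3.1.1 stratifies by clinical center only.

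**The concern.** The square root is meant to put eyes with small and large lesions on a common growth scale. For a single round lesion it does: the square root of the area is proportional to the radius, so a constant border advance gives a constant rate. For several lesions summed before the root is taken, it does not. Two eyes with the same total area and the same border advance then have different growth rates, because the eye with more lesions has more border.

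Entry admits eyes that differ in this respect, and neither the model nor the randomization takes account of it. Part of the between-eye variation that the analysis treats as noise would then be predictable from the baseline images. With about 21 completers per arm and a difference of 0.08 mm/yr as the worked example in 8.3, a wider interval than necessary weakens the go/no-go decision that the pilot is meant to inform.

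**Working it through.** **Inputs from 8.3.** 50 subjects, 15% dropout, one-sided 90% confidence, growth 0.40 versus 0.32 mm, SD of annual growth 0.20 mm.

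**Assumed, because the documents do not give them.** The share of multifocal eyes (30-60%), the lesion sizes and the border speed.

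**1. The plan's own figure.** 50 × 0.85 = 42.5 completers, or 21.25 per arm. Half-width in SD units: 1.2816 × √(2/21.25) = 0.393, or 0.400 with the t quantile. The stated 0.4 reproduces, and (0.40 − 0.32)/0.20 = 0.40. In mm with 21 per arm, the standard error is 0.20 × √(2/21) = 0.062 and the half-width is 1.2816 × 0.062 = 0.079 mm/yr.

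**2. Geometry.** For separate circles of radius rᵢ with a common border advance g, A = πΣrᵢ². Then d√A/dt = g√π × Σrᵢ/√(Σrᵢ²). The ratio to a single-lesion eye is R = Σrᵢ/√(Σrᵢ²), which is at most √n and equals √n for n equal lesions. Total area does not enter, so the root does remove size when the pattern is fixed.

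**3. Ratios.**
- Three equal lesions: √3 = 1.73, the maximum for three.
- Areas of 4, 0.5 and 0.5 mm²: (2 + 0.707 + 0.707)/√5 = 1.53.
- One dominant lesion (radii 2.185, 0.125 and 0.125 mm): 1.11 at baseline and 1.19 over 18 months at an assumed border speed of 0.15 mm/yr.
- Eyes entering by the small-lesion route, over 18 months at the same speed: radii 0.62, 0.30 and 0.20 mm give 1.62; radii 0.62, 0.125 and 0.125 mm give 1.49.
- Four equal lesions give 2.00 and five give 2.24.

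Untransformed area would not avoid the issue. There dA/dt = g × perimeter, and at equal total area three equal lesions have √3 times the perimeter of one.

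**4. Share of variance.** Let f be the multifocal share. Hold the overall mean at 0.40 mm/yr and the total SD at 0.20. The single-lesion mean is m₁ = 0.40/(1 − f + fR), the between-group variance is f(1 − f)[m₁(R − 1)]², and its share is that variance divided by 0.04.

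Example with R = 1.73 and f = 0.3: m₁ = 0.328 and the multifocal mean is 0.568, a difference of 0.240. The variance is 0.21 × 0.240² = 0.0121, a share of 30%. The residual SD is √(0.04 − 0.0121) = 0.167, and the half-width is 1.2816 × 0.167 × √(2/21) = 0.066.

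Over f = 0.3 to 0.6:

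| R | Share of variance | SD of chance imbalance between arms (mm/yr) | Adjusted half-width (mm/yr; unadjusted 0.079) |
|---|---|---|---|
| 1.2 | about 3% | about 0.011 | 0.078 |
| 1.53 | 16-18% | 0.024-0.026 | about 0.072 |
| 1.73 | 25-30% | 0.031-0.034 | 0.066-0.069 |

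The imbalance column is √(2 × between-group variance/21). It is a component of the standard error of 0.062, not an addition to it: at R = 1.73 and f = 0.3, 0.034²/0.062² is again about 30%.

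**The case against.** The strongest reply is that the plan contains no error here. Section 8.4 claims only to mitigate dependence on initial size, and at a fixed lesion pattern the root does that. Allocation is randomized 1:1, so leaving out a baseline predictor causes no bias in expectation. Which covariates to use in a 50-subject pilot is a design choice. All of this stands, and it limits the point to precision.

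Several stronger readings are tempting, but the documents do not support them.
- *A chance imbalance in focality would shift the ALA effect beyond what the plan allows for.* It would not. The 0.031-0.034 mm/yr is a partition of the same 0.20² that gives the planned standard error, so the interval already covers it.
- *Multifocal eyes typically grow 1.7 times as fast or more.* For three lesions 1.73 is the ceiling and requires equal, separate circles; anything higher needs four or more lesions. Merging lowers the ratio. The single-lesion means at R = 1.73 (0.278-0.328 mm/yr) imply border speeds of 0.157-0.185 mm/yr after division by √π. Two facing borders then close gaps of 0.47-0.56 mm in 18 months.
- *Entry consists of two distinct patterns.* Section 4.2.1 limits the largest lesion and allows any number of others, so eyes form a continuum.
- *Lesion count is already recorded for every eye.* Section 7.2.3 requires areas to be measured. The rule of at least three lesions applies only when the largest is below 0.5 DA, and no count field is named.

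It may also be said that the random effects deal with the matter. They carry differences between eyes as variance; they do not remove the part that lesion number predicts.

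**Conclusion.** The point holds as an inexpensive gain in precision. The transformation in 8.4 leaves a dependence on lesion number, entry lets lesion number vary, and nothing in the analysis or the stratification accounts for it. Validity is not affected, and the stated effect size of 0.4 reproduces.

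The size is uncertain. The half-width falls from 0.079 to 0.078 mm/yr if one dominant lesion is the rule, to about 0.072 at a ratio of 1.53, and to 0.066-0.069 at 1.73, which is a reduction of at most about 16% (1 − 0.066/0.079). These figures rest on separate round lesions, equal border advance, an assumed 30-60% multifocal share and 0.20 mm/yr as the total SD. Larger gains would need eyes with more lesions than three, and the documents give no lesion counts. If 0.20 is instead the SD within a focality class, the total SD at a ratio of 1.73 would be √(0.04 + between-group variance), about 0.22 to 0.23, and the unadjusted interval would be wider than planned.

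**What to change.** In 8.4, pre-specify baseline focality of each study eye (one versus several lesions, derived from the Reading Center's baseline FAF grading) and its interaction with time as fixed effects in the main mixed model. State that the model is fitted to the square root of total area. The interaction is the term that matters for slopes, because focality acts on the growth rate. Include the same covariate in the preliminary 18-month comparison; this means a regression that accounts for two eyes per subject in place of the t-test variant. Focality is an eye-level covariate, so a subject's two study eyes may differ.

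The cost is one or two degrees of freedom, some sentences in 8.4, and the derivation of a lesion count that the protocol does not name as a recorded field. The endpoint, eligibility, visits and randomization do not change. The gain will be small if most eyes have one dominant lesion. The term should be fixed before treatment assignments are known to the analysts, because adding it after an imbalance has been seen would be open to challenge.

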Intervention Phase

The Coordinating Center is responsible for random assignment of patients to one of the two treatment groups. Random treatment allocation schedules will be generated using a randomized block design and stratified by clinical center. All baseline procedures must be performed within 40 days of the day of randomization.

For subjects who have successfully completed the run-in phase, the clinical site will inform the Coordinating Center that that all inclusion and exclusion criteria have been met. Coordinating Center staff will issue the next randomized treatment assignment from the clinical site's schedule for the patient. A Coordinating Center staff member notifies the clinical site Investigator that the randomization has been completed and the Investigator will fax/send a prescription for study medication (ALA or placebo), signed by the Principal or Sub-Investigator, to the University of Pennsylvania's Investigational Drug Service (IDS). A Coordinating Center staff member will notify IDS of the treatment assignment.

Once IDS receives both the prescription from the Investigator and the treatment assignment from the Coordinating Center, IDS will send a supply of study drug to the subject's home. Subsequent study medication also will be mailed by IDS directly to the subject's home.

For both study Phases, prior to starting the medication, the subject will be instructed on how to take the medication, and what signs and symptoms to monitor and report. For Phase 2 of the protocol, each subject will be contacted approximately two weeks after randomization to verify that the study drug has been received and that each subject is taking the study medication per instructions.

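### Randomisation is stratified by clinical center, but no analysis in section 8.4 names center and the preliminary BCVA comparison omits baseline BCVA; nothing is biased and the cost is small (optional)

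*Combined protocol and SAP*

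**What the plan says.** On allocation, section 3.1.1 (Intervention Phase) says: "Random treatment allocation schedules will be generated using a randomized block design and stratified by clinical center".

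On analysis, section 8.4 describes two layers for Phase 2.

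- **Preliminary.** Mean 18-month changes in GA area and in visual acuity, and some proportions, are compared between arms. The methods are given as "Variants of the independent t-test and chi-square tests of proportions that account for the correlation between eyes of subjects who have two study eyes". For area, "a square root transformation will be applied to the area measurements to mitigate the dependence of growth rate on initial size". No baseline value and no center term is mentioned.
- **Main.** "The main analysis for comparing treatment groups will compare the rates of change in total area of GA using a mixed effects linear model". The only model terms named are random ones: "Both subject and eye will be considered random effects". The fixed effects are not listed beyond what a comparison of rates implies.

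For everything else, "Similar analytic methods using mixed effects models will be used for the other outcome measures", again without stated terms. Center appears in no analysis in 8.3 or 8.4.

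Section 8.3 frames the result as a one-sided 90% confidence limit. With 50 subjects and 15% dropout, the limit is 0.4 in standard deviation units. The worked example is 0.40 against 0.32 mm "when the standard deviation of the annual growth rate is 0.20 mm". The possible halt condition is a sign: "if the observed growth rate in the actively treated group is greater than in the placebo group".

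**The concern.** When allocation is stratified and blocked, the arms are balanced within each center, so the true sampling spread of the treatment difference excludes most of the between-center variation. An analysis without center leaves that variation in the residual. The reported standard error then does not credit the balance that the design created. In a trial whose product is the width of a one-sided limit, it is reasonable to ask how much width is lost.

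A second gap concerns BCVA. A two-sample test of change is less precise than an analysis adjusted for the baseline value unless baseline and final values are very highly correlated. Baseline BCVA is collected on every subject. For GA area the plan has already acted on initial size through the square root, so the same argument has little force there.

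There is also a question of pre-specification. With center unmentioned, the model could be fitted with or without it after the data are seen, and the two fits give slightly different limits.

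**Working it through.** **Inputs from the documents.** 50 subjects, 1:1 (3.1); 15% dropout, one-sided 90%, limit 0.4, SD 0.20 mm per year (8.3); four clinical sites in 3.1, five in the Study Summary; 10 to 15 subjects expected per site (4.2.5), with no cap per site (7.1).

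**Assumed, because the documents do not give them.** Share of outcome variance due to center (R²) 0 to 0.10; block size 4; baseline-to-18-month BCVA correlation r of 0.5 to 0.9; equal variances at the two times.

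**Step 1: the plan's figure.** 50 × 0.85 = 42.5 subjects. Normal quantile: 1.282 × √(4/42.5) = 0.393. With t and 21 per arm: t(0.90; 40) × √(2/21) = 1.303 × 0.3086 = 0.402. The stated 0.4 reproduces without a center term. The example agrees: (0.40 − 0.32)/0.20 = 0.4.

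**Step 2: center.** Simulation with stratified blocks, random dropout, one value per subject, total variance 1 and 6,000 runs per setting, fitted by least squares without and with center. Four centers of 13, 13, 12 and 12:

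| Center R² | Half-width without | Half-width with | Ratio | True SD without / with |
|---|---|---|---|---|
| 0 | 0.399 | 0.403 | 1.009 | 0.308 / 0.310 |
| 0.02 | 0.399 | 0.399 | 1.000 | 0.307 / 0.309 |
| 0.05 | 0.396 | 0.392 | 0.988 | 0.304 / 0.306 |
| 0.10 | 0.394 | 0.381 | 0.968 | 0.292 / 0.292 |

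Five centers of 10 give ratios 1.015, 1.008, 0.995 and 0.971. Unequal centers (24/12/10/4 and 20/12/9/6/3) give 1.009 to 0.973 and 1.016 to 0.977. The break-even R² is about 0.02 with four centers and 0.04 with five.

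The last column shows that the true spread of the estimate hardly changes; what changes is the reported limit. With four centers, coverage of the limit without center was 0.898 to 0.907 against 0.90.

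In millimetres, four centers: (0.4026 − 0.3992) × 0.20 = 0.0007 mm per year wider at R² = 0, and (0.3936 − 0.3810) × 0.20 = 0.0025 mm per year narrower at R² = 0.10. The example effect is 0.08 mm per year. This conversion assumes the square-root scale and one slope per subject.

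**Step 3: bias and sign.** With a true effect of −0.400, the mean estimate without center lay between −0.397 and −0.403 for R² of 0 to 0.20. With no true effect, the adjusted and unadjusted estimates had opposite signs in about 4 to 7% of trials.

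**Step 4: baseline BCVA.** The ratio of the ANCOVA half-width to the change-score half-width is √[(1 + r)/2 × (1 + 1/38)] × t(0.90; 39)/t(0.90; 40).

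- r = 0.5: √(0.75 × 1.0263) × 1.0004 = 0.878
- r = 0.8: √(0.90 × 1.0263) × 1.0004 = 0.961
- r = 0.9: √(0.95 × 1.0263) × 1.0004 = 0.988

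If four centers are also fitted and explain nothing, simulation gives 0.886, 0.970 and 0.996 at the same correlations and 1.011 at r = 0.95, with break-even near 0.91.

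**Step 5: baseline area.** Take growth at the plan's figures, independent of initial size, with square-root areas spread uniformly over the eligible range (1.25 to 15.0 mm²). The correlation between square-root change and baseline is then essentially zero, so a baseline covariate gains nothing. On untransformed area the same example gives about 0.44.

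**The case against.** The strongest reply is that this is a preference, not a defect. The estimate is unbiased and the limit errs, if at all, on the safe side. One reading center grades all images (7.2.1), so large center differences in measured area are not to be expected; at a small R² the center term changes nothing or widens the limit by about 1%. The BCVA gain is for a secondary endpoint in a comparison labelled preliminary, with mixed models already promised for the other outcomes. All of that stands and is why the point is optional.

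Three technical replies also stand.

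- The center figures come from one value per subject, not from the longitudinal model with two eyes in some subjects. They indicate size only.
- Section 8.4 attaches the square root to the preliminary analysis and does not repeat it for the main model, so the conversion to millimetres rests on an assumption.
- Clustered standard errors need a small-sample correction. In a check with about 42 subjects, 40% with two eyes and between-eye correlation 0.7 (all assumed), nominal 0.90 limits covered 0.87 to 0.88 uncorrected and 0.88 to 0.89 corrected.

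A reader might infer that ignoring the strata biases the estimate or inflates the error rate. The calculations show no bias, and coverage at or slightly above nominal. A reader might also infer that baseline area is wrongly missing from the main model. In a model of area over time, the baseline area would normally be the time-zero response, and nothing in 8.4 says otherwise.

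**Conclusion.** The omission is real: allocation is stratified by center, no stated analysis uses center, and the preliminary test of BCVA change ignores baseline BCVA. The consequence is minor. The one-sided 90% limit without center is neutral to mildly conservative. Adding center moves its width from about 1 to 1.5% wider to about 3% narrower over an assumed R² of 0 to 0.10. If R² were as high as 0.20, the standard error would fall by about 8%, but nothing in the documents points to that.

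The sign on which a halt might rest is unbiased either way. It would be too strong to say that it cannot change, since the two analyses can disagree when the observed difference is close to zero.

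For BCVA change, the gain from baseline alone is about 12% to 1% of the width at r from 0.5 to 0.9, and essentially nil above that. No gain is shown for square-root area. The remaining benefit is that the terms are fixed before anyone sees the data. The comparisons of proportions are not part of this point. Severity: optional.

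**What to change.** In section 8.4:

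1. List the fixed effects of the main mixed model as treatment, time, treatment-by-time, clinical center and center-by-time. The last term matters because, with subject random effects, a center main effect mostly shifts levels rather than slopes. State the scale of the response.
2. Give a rule for pooling very small centers, fixed before unblinding, since 7.1 leaves site sizes unrestricted. Reconcile the four and five site counts at the same time; the conclusion is the same with either.
3. Replace the preliminary t-test of BCVA change with ANCOVA on baseline BCVA and center, handling two-eye subjects with a subject random effect or clustered standard errors with a small-sample correction.
4. Leave the preliminary square-root area comparison without a baseline covariate.

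The cost is wording only. Center and baseline BCVA are already known for every subject, and neither sample size nor procedures change. The statistical price is a few degrees of freedom: the main limit is about 1% wider with four centers, or 1.5% with five, if center explains nothing. The BCVA limit would be about 1% wider at a correlation of 0.95.
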